4.2 Exclusion Criteria

1) male (While we are aware of the NIH preference for studying men with BC, there presence would likely reduce the feeling of safety within the groups due to the sensitive subject matter); 2) lifetime history of bipolar disorder, schizophrenia, schizoaffective disorder or with a pre-cancer diagnosis of fibromyalgia or chronic fatigue syndrome 3) active suicidal plan (will ensure immediate intervention); 4) dementia/other disorder that would preclude informed consent or comprehension of assessments; 5) Individuals taking anticholinergic medications, and post myocardial infarction (6 months before recruitment) or with a pacemaker, which would render the

metric of HRV invalid. 6) Flare-up in systemic autoimmune disease (such as arthritis, lupus or multiple sclerosis), thyroid dysfunction that requires increases in medication

We will inquire about and document any illness in the previous week with infection or acute viral disease as well as having dental work⁶³ to account for these in our analyses. Additionally, should we encounter 6 or more men with BC we will conduct an Art Therapy intervention group for qualitative data gathering.

After assessing eligibility and providing verbal consent to be contacted the site nurse will document their contact information in the Screening Log. The research coordinator will contact the potential participant by phone and will schedule a face to face meeting with the eligible participant. During the face to face meeting the research coordinator will use the following script to inform the eligible participant about the study:

5. STUDY INTERVENTIONS

5.1 Interventions, Administration, and Duration

Both interventions will be administered in a group format by a trained individual. Each session will be 1.5 hours (intervention) and an hour (comparison) once a week for 8 weeks. There is a risk of participants feeling distress due to the exposure to emotional content either discussed in the group or that arises in the art therapy intervention group. The psychosocial team at each study site will be prepared to meet with any participant who requests so. Interventionists will be trained to identify and refer distressed participants to the psychosocial team.

5.2 Handling of Study Interventions

Participants will be blinded to whether they are receiving the intervention or comparison group. The treatment protocol derives its theoretical framework from the Bodymind model of AT⁶² and from the application of Focusing to Art Therapy^{64,65} for the purpose of body awareness and developing a focusing (“being friendly, accepting, non-judgmental and welcoming to one’s inner felt sense”)⁶⁶. All sessions start with a ten-minute rapport building and touching base and continue with 50 minutes of art making in a calm and supportive environment. Art materials are on the table and after the art therapist provides a brief explanation of the use of the materials; participants are encouraged to explore and experience as they wish. Group leader is present to guide and assist. The role of the art therapist is to encourage a non-judgmental and exploratory approach to artmaking in which the process is emphasized over product. The art therapist obtains these goals by creating an atmosphere that is calm and by remaining tuned in to the verbalizations and body language of participants. If needed she can provide individual attention that is geared toward neutralizing concerns regarding performance during the art making. This approach is defined as providing a “Third-hand”⁶⁷: assisting in problem solving and dilemmas related to the

[figure not shown]

Figure 1: Flow chart of time-points

art making process. The art therapist encourages participants to refrain from conversation and instrumental music is played to encourage introspective experiences. The session ends with 30 minutes of processing and discussion in which the art therapist requests each participant to share and briefly presents their work and group participants can respond and or provide support. The art therapist will remind group members to be respectful and non-judgmental toward other participants and themselves.

Session 1: getting familiar and safe: An introduction to the group, the group leader will speak about motivation for exploration via art and remaining open to new experiences. The leader will introduce the art materials and art making from a non-judgmental stance and the importance of process of product. The concept of safe place will be introduced to the group and members will be asked to create a safe place via art. The goals of this session: Rapport Building, Contract Building and getting familiar and comfortable with the art materials.

Session 2: Art making will be exploratory in the framework of open studio in which a specific topic is not provided and participants are encouraged to explore the art materials. The goal of this session is to provide an experiential encounter with the art making process. There will be a 10-minute Psychoeducation presentation on the nature of emotions at the beginning of the session.

Session 3: Group members will introduce themselves to the group by making a drawing about an emotion. The goal of this session is to continue learning on the nature of emotions and increase awareness of emotion responding patterns.

Session 4: The art therapist requests the participants to create an image of somethings that is distressful to them and sit with it for a while. Then, they are requested to create an additional drawing that changes one element of the distress drawing, a feature, a color, a shape, or just a change in composition. The images are discussed among group members and implications for real life situations are discussed. The goal of this session is twofold- to identify the location of distress in the body, increase distress tolerance, cognitive flexibility and reframing.

Session 5: This session is open studio in which participants are encouraged to engage freely with the art materials. The goal of this session is to help participants identify how they react and respond to their emotions and bring an awareness of emotional experiences and learn the skill of "Clearing the Space"-using artmaking to identify feelings and experiences without the need to identify with them.

Session 6: Clients are requested to draw two sides of a current conflict in their life. It can be something small, like deciding where to go for lunch, or something large, like which treatment to

engage in. All conflicts are welcome, but it should have significance to its creator and be something that they are struggling with and would like to learn more about. After the drawing period, clients are requested to look at both options and examine their sensations, feelings and thoughts about each. Their art, thoughts and feelings are shared with the group. The goal of this session is to increase cognitive flexibility and reframe. This means that through creating 2 pictures participants will be able to view a situation from 2 points of view and identify more than one option for coping with the conflict they presented.

Session 7: Body image: In this module participants will create art using body outline templates as a framework for art making. The goal of this session is to increase introceptive awareness and assist in processing emotional content from implicit experience to explicit expression. Distress tolerance.

Session 8: Summary: This session will be a summary of all that has been experienced and clients will be provided with a letter that summarizes their progress. Each client will receive a package of oil pastels and blank journal for the encouragement of their continued process at home. The goal of this session is to review achievements and encourage incorporating what was learned in day to day life after the intervention is over.

The comparison group is designed to control for the impact of the aspect of the group experience that are not explicitly focused on emotional processing, ie, the time with art materials and focused attention aspects that occur during an Artmaking session. These sessions will not have a rapport building component and will include 40 minutes of coloring pre-fabricated shapes (Mandalas- see figure 3) in a calm environment and 20 minutes of self-care instruction. Coloring Mandala's has been demonstrated to reduce anxiety⁶⁸⁻⁷⁰. Participants are encouraged to minimize conversation; instrumental music is played to encourage introspective experiences. Due to our concerns that participants will become bored after more than 40 minutes of coloring we will not be equally comparing the amount of time that participants are together in the group format.

Figure 3: Mandala example

5.3 Concomitant Interventions

5.3.1 Allowed Interventions

Any standard medical treatment for cancer is allowed (i.e., surgery, chemotherapy, radiotherapy,

neo-adjuvant chemotherapy, endocrine therapy). However, participants should not be on chemotherapeutic agents during the study period.

5.3.2 Prohibited Interventions

Participants should not be engaged in another form of Psychotherapy or support group at the time of the intervention. Anticholinergic medications and beta-blockers are prohibited as they render the HRV and cytokine measures invalid.

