3. STUDY DESIGN

We will accomplish the aims by a randomized controlled trial of 240 Jewish and Arab women (>18 years) who have been diagnosed with BC and have completed chemotherapy, recruited in Israel and randomized to undergo an 8-week (1.5 hours per week) program of group Art Therapy compared to women who will be designated to an 8-week sham Art Therapy group. We chose this design to be able to isolate and examine emotional processing and the effect of enhancing emotional processing on HRV and inflammatory cytokines and examine how these may mediate the effect of art therapy on depressive symptoms, pain and fatigue.

The primary outcomes are emotion processing, comprised of emotion awareness, expression and acceptance and the cholinergic anti-inflammatory pathway, comprised of resting HRV and inflammatory (pro and regulatory) cytokines. The secondary outcome measures are depression, pain and fatigue.

The study will take place at the cancer centers of 3 study sites: Rabin Medical Center, Rambam Medical Center and Ziv Medical Center, the enrollment period will vary until each cohort is collected and is expected to be approximately a month or a month and a half.

The interventions will be administered by an experienced Art Therapist who will be trained in this specific protocol by the PI [name] who is an Art Therapy [name] intervention is designed to follow the Bodymind model of AT⁶². Each session will start with a ten-minute rapport building and touching base and continue with 50 minutes of art making in a calm and supportive environment. Art materials are on the table and after the art therapist provides a brief explanation of the use of the materials; participants are encouraged to explore and experience as they wish. The art therapist is present to guide and assist. Participants are encouraged to minimize conversation; instrumental music is played to encourage introspective experiences. The session ends with 30 minutes of processing and discussion in which each participant shares and briefly presents their work and group participants can respond and or provide support.

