4.1 Inclusion Criteria

1) adult (>18) females with initial or recurrent BC; 2) study entry within one year of diagnosis and 3 months after adjuvant cancer care (chemotherapy and radiotherapy (RT)) or reconstructive surgery; any additional or replacement standard medical treatment for cancer is allowed (i.e., surgery, chemotherapy, radiotherapy, neo-adjuvant chemotherapy, endocrine therapy); 4) additional medication is allowed, excluding what is described in exclusion criteria, and will be assessed for potential inclusion as a covariate; 5) can complete assessments in Arabic or Hebrew; 6) provides informed consent.

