6. STUDY PROCEDURES

6.1 Schedule of Evaluations

Assessment	Screening Visit-1 (Day-14 to Day-1)	Baseline Visit 1 (Day 0)	Tx Visit 2 (W1)	Tx Visit 3 (W2)	Tx Visit 4 (W3)	Tx Visit 5 (W4)	Tx Visit 6 (W5)	Tx Visit 7 (W6)	Tx Visit 8 (W7)	Tx Visit 9 (W8)	Tx Visit 10 (W9)	Follow-up Final Visit (W16)
Verbal consent	X											
Informed Consent Form		X										
Demographics	X											X
Medical Chart Review	X											
Current Medications	X	X										
Inclusion/Exclusion Criteria	X											
Enrollment/ Randomization		X										
Adverse Events		X	X	X	X	X	X	X	X	X	X	
Questionnaires		X								X	X	
Heart measurement rate		X								X	X	
Blood draw		X								X		

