6.2 Description of Evaluations

6.2.1 Screening Evaluation

During clinic hours, research staff at the oncology practices will introduce potentially eligible patients to the study using a verbal script. Interested patients (having received a letter, flyer or referral) will call our office and receive an initial phone screening to assess age, stage, and Hebrew or Arabic language use. If initial criteria are met, an in-person visit will be scheduled either in our University office or at one of the 3 hospital recruitment sites where private rooms are arranged, depending on convenience to prospective participants to complete evaluation of eligibility, including major clinical depression, detailed medical history and current medications.

Consenting Procedure

The research nurse will obtain verbal consent from the patient agreeing to participate in the screening session. During the screening session, there will be a single informed consent form that describes both the screening and study procedures. Once eligibility is established, Subject's Consent Form and Health Information Privacy Protection Act (HIPAA) information will be reviewed and, if consenting, participants will sign. Each site will have a designated MD or nurse to review documents related to medical and symptom-based eligibility criteria. Informed consent will be documented on a University of Haifa Ethics committee-approved form. A copy of the signed form will be given to the subject. Signed consent forms will be kept in [name] office,

which is an administrative office separate from research data and available for audit even when the PI is not. Additional information contained in a case book will be relevant demographic and medical/psychiatric information about the subject obtained during the interview with the site representative. Because this case book will contain personal identifiers and PHI, it will be kept separate from any data gathered as part of the study, and will be kept in a locked office. After consent is obtained, potential subjects will be screened by study personnel to determine that the subject meets all inclusion and exclusion criteria for study participation.

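### Sections 4.1, 4.2 and 5.3.2 contradict each other on beta-blockers, so eligibility screening as written can admit women whose HRV and cytokine data the protocol calls invalid

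*Protocol*

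**What the plan says.** Four parts of the protocol bear on this point.

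- **5.3.2 Prohibited Interventions:** "Anticholinergic medications and beta-blockers are prohibited as they render the HRV and cytokine measures invalid". The sentence gives no date or visit from which the prohibition applies.
- **4.2 Exclusion Criteria, item 5** excludes "Individuals taking anticholinergic medications, and post myocardial infarction (6 months before recruitment) or with a pacemaker", on the ground that these would make the "metric of HRV invalid". Beta-blockers are not in the list, and cytokines are not part of the reason.
- **4.1 Inclusion Criteria, item 4:** "additional medication is allowed, excluding what is described in exclusion criteria, and will be assessed for potential inclusion as a covariate".
- **6.2.1 Screening Evaluation:** "potential subjects will be screened by study personnel to determine that the subject meets all inclusion and exclusion criteria for study participation". Section 9.2 describes the same check. Neither section names 5.3.2.

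Section 3 makes "the cholinergic anti-inflammatory pathway, comprised of resting HRV and inflammatory (pro and regulatory) cytokines" a primary outcome domain alongside emotion processing. In the schedule in 6.1, "Current Medications" is marked at Screening and Baseline only. Section 6.2.4 plans HRV recording and blood collection at both T2 and T3 and lists no medication question there. Beta-blockers are mentioned nowhere else in the protocol or the SAP.

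**The concern.** The protocol treats the same drug in two incompatible ways. Under 4.1 it is permitted and may become a covariate. Under 5.3.2 it is prohibited because it invalidates the measurement. A covariate can adjust for a shift in level, but it does not repair a measurement declared invalid, so the two treatments cannot both stand.

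What is at stake is the content of the HRV and cytokine analyses. Three hospitals recruit, each with its own nurse identifying candidates. One site could screen on 4.1 and 4.2 while another also applies 5.3.2, and the enrolled populations would then differ by site. No medication check is scheduled after baseline, so a listed drug started or stopped between assessments would not be recorded. The SAP has no rule for records taken on a prohibited drug; the only covariate it names is traditional values, under Hypothesis 3.

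**Working it through.** **Step 1: the three rules applied to one woman who takes a beta-blocker and is otherwise eligible.**

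| Section | Result |
|---|---|
| 4.2 item 5 | Not excluded, because the drug is not listed |
| 4.1 item 4 | Allowed, because it is outside the exclusion criteria; possible covariate |
| 6.2.1 and 9.2 | Passes, because the check covers inclusion and exclusion criteria only |
| 5.3.2 | In breach; her HRV and cytokine measures are called invalid |

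She is eligible and in breach on the same day. No figure is needed to establish this.

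**Step 2: the plan's own power figure.** Protocol 8.2 and SAP C.5.1 state more than 90% power for d = 0.50 on the mechanisms with 120 women per condition. Alpha is not stated, so two-sided 0.05 is assumed. With the normal approximation:

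power = Φ(d × √(n/2) − 1.96) = Φ(0.5 × √60 − 1.96) = Φ(1.913) = 97.2%.

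The stated figure is reproduced.

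**Step 3: how far beta-blocker use could erode it.** The share of users is not in the documents, so a range q is assumed. Three cases are shown:

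- (a) Users' data are dropped: n = 120 × (1 − q) per arm.
- (b) As (a), with 15% attrition also removed: n = 120 × (1 − q) × 0.85. The 15% comes from the protocol's Sample Size and Population paragraph. Taking it off the 240 is the cautious reading, since the same paragraph gives a target of 300.
- (c) Users are kept and assumed to show no treatment effect: d = 0.5 × (1 − q), n = 120.

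| Assumed share q | (a) | (b) | (c) |
|---|---|---|---|
| 0% | 97.2% | 94.6% | 97.2% |
| 5% | 96.5% | 93.6% | 95.7% |
| 10% | 95.7% | 92.3% | 93.7% |
| 15% | 94.6% | 90.9% | 90.9% |
| 20% | 93.4% | 89.1% | 87.3% |
| 30% | 90.0% | 84.8% | 77.4% |

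Worked example, 15% in case (a): n = 102, Φ(0.5 × √51 − 1.96) = Φ(1.611) = 94.6%.

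Up to a 15% share, power stays above 90% in all three cases. It falls clearly below 90% only at larger shares combined with attrition or with full dilution.

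**Step 4: where validity could still suffer.** Hypothesis 1 is tested by Time × Condition. Use that is stable and present before randomisation is balanced between arms in expectation, so it would mainly add noise or attenuate the effect. The mediation analysis in SAP C.5.2 is less protected. Path b relates change in the physiological measures to change in symptoms and is not randomised, so a drug started or stopped between assessments could distort those change scores.

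**The case against.** The strongest reply is that 5.3.2 can itself be applied at entry. It says the drugs are prohibited, without a start point; only the sentence on psychotherapy is limited to the time of the intervention. Section 6.2.1 includes current medications in the in-person evaluation of eligibility, the schedule records them at Screening and Baseline, and 6.2.2 places randomisation after the baseline visit. A site reading the whole protocol has two chances to identify a user before she is randomised. This stands: enrolment of users is possible, not inevitable. It does not remove the contradiction, because nothing requires a site to read 5.3.2 that way and 4.1 refers only to the exclusion criteria.

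It is also fair to say that 4.1 provides partial handling through covariate assessment, and that randomisation balances baseline use in expectation. Both points reduce the likely bias between arms. Neither answers the protocol's own word, invalid.

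Stronger readings are tempting, and the documents do not support them:

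- *A prescribed cardiac drug would have to be stopped after entry.* No section says so; this would be inferred from silence.
- *Between 12 and 36 women will have invalid data.* These figures are 0.05 × 240 and 0.15 × 240. They rest on an assumed 5–15% share and on no site applying 5.3.2 at entry, so they are at most a conditional upper bound.
- *Half of the primary outcomes are invalid.* Only HRV and cytokine records from users who are actually enrolled would be affected.

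**Conclusion.** The point holds as an internal contradiction. Sections 4.1, 4.2 and 5.3.2 give different answers for a woman on a beta-blocker, and the eligibility check as written follows the two that admit her. Her HRV and cytokine data would then be invalid by the protocol's own statement, in one of the two primary domains.

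The number of women affected cannot be derived from the documents. A reader might infer that the trial becomes underpowered. Under the assumptions above (two-sided alpha 0.05, normal approximation, d = 0.50), the stated power above 90% is largely preserved. The issue is therefore the validity of these records and consistent eligibility across sites. Confidence is high for the contradiction itself and lower for its practical effect, which depends on how sites act and how common use is. The sponsor should correct it.

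**What to change.** 1. **Reconcile 4.1, 4.2 and 5.3.2** so that the same list of drugs applies at screening and during the study. Its content, and any clinical handling of a woman who takes or starts a listed drug, are for the sponsor's clinicians to decide.
2. **Repeat the current-medication question at T2 and T3**, where HRV and blood are already planned, and add it to the schedule in 6.1.
3. **Flag** each HRV and cytokine record taken on a listed drug.
4. **Add to the SAP** a sensitivity analysis that runs the HRV and cytokine models with and without flagged records. It should separate use recorded before randomisation from use that began afterwards. Excluding records for drugs started after randomisation conditions on a post-randomisation event and can break the randomised comparison, so the SAP should say so and those results should be read with that caution.

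The cost is a wording change in three sections, one repeated question at two existing assessments, and one additional analysis. The sample size does not change.

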5.4 Fidelity Assessment

Adherence to the study regimen will be defined as attending 80% of the group sessions, which will be monitored and recorded by the interventionist. The moderation of the effect of attending less than 80% will be assessed and dealt with during data analysis. Furthermore, fidelity of the intervention itself will be ensured by scoring the sessions against the treatment manual and observational fidelity checks by the gold standard rater (PI [name] initially and then trained PhD student 20% of sessions). Fidelity below an average of 4 will indicate the need for further training of the interventionist.

	1 not at all	2 a little bit	3 neither yes or no	4 quite a bit	5 very much so	Not applicable
1. Was there a sense of calm in the room?	1	2	3	4	5	N/A
2. Did you feel like you were able to support the participants?	1	2	3	4	5	N/A
3. Were the participants deeply engaged in art making?	1	2	3	4	5	N/A
4. Was the session divided in to 10-minute intro, 60 minutes art making and 20 minutes discussion?	1	2	3	4	5	N/A
5. Was the art making done with minimal conversations?	1	2	3	4	5	N/A
6. Was the group discussion respectful and safe?	1	2	3	4	5	N/A

